814 The treatment groups are as follows: 815 Group A: Sham + intravitreal ranibizumab 0.3 mg • Group B: Intravitreal dexamethasone +intravitreal ranibizumab 0.3 mg 816 • For both treatment groups, the initial ranibizumab injection must be given on the day of 817 818 randomization. The sham or dexamethasone injection will be given within 0-8 days of the 819 ranibizumab injection. If the injections are given consecutively on the same day, the sham 820 injection must be given first in Group A and the ranibizumab injection must be given first in 821 Group B. 822 823 Focal/grid laser is not permitted in the study eye. 824 825 4.6 Follow-Up Study Visits During the Randomization Phase The schedule of protocol-specified follow-up visits post-randomization is as follows: 826 827 828 • 4 weeks (± 1 week) 829 • 8 weeks (± 1 week) 830 • 12 weeks (± 1 week) 831 • 16 weeks (± 1 week) 832 • 20 weeks (± 1 week) 833 • 24 weeks (±1 week)– primary outcome visit 834 835 A minimum of 21 days is required between injections. An additional visit may be required for 836 completion of the second (steroid/sham) injection at randomization and 12 weeks. 837 838 4.7 Follow-Up Testing Procedures During the Randomization Phase 839 The following procedures will be performed at each protocol visit unless otherwise specified. A 840 grid in section 1.3 (J) summarizes the testing performed at each visit. 841 842 Visual acuity testers (including refractionist) and OCT technicians will be masked to treatment 843 group at the primary outcome visit (24 weeks). 844 845 1. Best-corrected E- ETDRS visual acuity testing in each eye A protocol refraction in the study eye is required at all protocol visits. Protocol refraction 846 • 847 in the non-study eye at the 24 week-visit only. When a refraction is not performed, the 848 most-recently performed refraction is used for the testing. 849 2. OCT on the study eye 850 3. Ocular exam on the study eye, including slit lamp examination, lens assessment, 851 measurement of intraocular pressure and dilated ophthalmoscopy 852 853 All of the testing procedures do not need to be performed on the same day, provided that they are 854 completed within the time window of a visit and prior to initiating any retreatment. 855 856 Testing procedures at unscheduled visits are at investigator discretion. However, it is 857 recommended that procedures that are performed should follow the standard DRCR.net protocol 858 for each procedure. If the study participant returns following a protocol visit specifically to 859 receive a study injection, testing prior to the injection is at investigator discretion. 860

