 - 995
 - 996 Study participants who withdraw will be asked to have a final closeout visit at which the testing
 - 997 described for the protocol visits will be performed. Study participants who have an adverse effect
 - attributable to a study treatment or procedure will be asked to continue in follow-up until the
 - 999 adverse event has resolved or stabilized.
 - 1000
 - 1001 Study participants who withdraw or are determined to have been ineligible post-randomization
 - 1002 will not be replaced.
 - 1003

1004 **5.8 Discontinuation of Study**

- 1005 The study may be discontinued by the Executive Committee (with approval of the Data and
- Safety Monitoring Committee) prior to the preplanned completion of follow-up for all studyparticipants.
- 1008

1009 **5.9 Contact Information Provided to the Coordinating Center**

- 1010 The Coordinating Center will be provided with contact information for each study participant.
- 1011 Permission to obtain such information will be included in the Informed Consent Form. The contact
- 1012 information may be maintained in a secure database and will be maintained separately from the
- 1013 study data.
- 1014
- 1015 Phone contact from the Coordinating Center will be made with each study participant in the first
- 1016 month after randomization and prior to the 24-week visit. Additional phone contacts from the
- 1017 Coordinating Center will be made if necessary to facilitate the scheduling of the study participant
- 1018 for follow-up visits. A participant-oriented newsletter and/or study logo item may be sent during
- 1019 the study.
- 1020
- 1021 Study participants will be provided with a summary of the study results in a newsletter format 1022 after completion of the study by all participants.
- 1023

1024 5.10 Study Participant Reimbursement

- 1025 The study will be providing the study participant with a \$25 gift card per completed protocol
- 1026 visit. Additional travel expenses will be paid in select cases for participants with higher
- 1027 expenses.

1028 1029	Chapter 6. ADVERSE EVENTS
1030	
1031	6.1 Definition
1032	An adverse event is any untoward medical occurrence in a study participant, irrespective of
1033	whether or not the event is considered treatment-related.
1034	
1035	6.2 Recording of Adverse Events
1036	Throughout the course of the study, all efforts will be made to remain alert to possible adverse

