1275 The estimation of treatment group difference in mean change in visual acuity from randomization 1276 to the 24-week visit will be performed using an analysis of covariance (ANCOVA) model, with the change in visual acuity measurements at 24 weeks fitted as the dependent variable, and the 1277 1278 treatment group as the independent variable, adjusting for the randomization stratification factor, and for the baseline measurement (visual acuity value at randomization visit) by including each as 1279 a covariate in the model. The treatment effect will be reported as the mean difference (and standard 1280 1281 deviation) between treatment groups in change of visual acuity letter score from randomization to 24-week visit with 95%CI from ANCOVA model. The significance level used for the final primary 1282 1283 analysis will be 0.05. The study is not powered to establish treatment efficacy; however, treatment comparison will be conducted for visual acuity and OCT retinal thickness outcomes to assess 1284 1285 treatment effect.

1286

1288

1289

1287 There will be two analyses: an "intent-to-treat" analysis (ITT) and a "per-protocol" analysis:

- The intent-to-treat analysis will include all randomized eyes. Rubin's multiple
 - imputation method will be used to impute missing data at the 24-week visit.

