1290 The per-protocol analysis will be performed including only participants who complete all • 1291 required injections without receiving any non-protocol treatments and have data at the 1292 24-week visit. 1293 • The intent-to-treat analysis is considered the primary analysis. If the intent-to-treat and 1294 per-protocol analyses yield the same results, the per-protocol analysis will be used to provide supportive evidence of the magnitude of treatment effect among patients who 1295 received the treatment. If the results of the two methods differ, exploratory analyses will 1296 1297 be performed to evaluate the factors that have contributed to the differences. A sensitivity analysis will be conducted to compare the results from multiple imputation with those 1298 1299 using a per-protocol analysis only including study participants who completed the 24-1300 week visit and with results from last-observation-carried-forward. 1301 1302 Generalized estimating equations (GEE) will be used to adjust for the correlation between eyes 1303 of patients who have two study eyes. 1304 1305 Although expected to be under-powered, pre-planned subgroup analyses will be conducted in the same way as the primary analysis and include stratification by improvement in OCT CSF thickness 1306 during run-in phase visits by $\geq 10\%$ at any visit, and improvement in VA during run-in phase by 5 1307 or more letters at any visit. Other subgroup analyses will be described in the detailed Statistical 1308 1309 Analysis Plan. These subgroup analyses will be used to guide choice of pre-planned subgroup 1310 analyses in the phase III trial. 1311 1312 Imbalances between groups in important covariates are not expected to be of sufficient magnitude 1313 to produce confounding; however, a second analysis that adjusts for imbalanced baseline covariates will be performed. If results are similar to the primary analysis, the primary analysis 1314 will be accepted as the definitive analysis; otherwise, the reasons for the difference will be 1315 1316 explored. 1317 1318 There are no data to suggest that the treatment effect will vary by sex or race and ethnicity. 1319 However, both of these factors will be evaluated in exploratory analyses. 1320 1321 7.4 Secondary Outcomes 1322 In addition to the primary outcome, the following secondary outcomes will be estimated, and their 1323 95% CI will be obtained in each treatment group and compared between treatment groups: 1324 1325 • Percent of eyes with at least 10 and at least 15 letter gain (increase) or loss (decrease) in E-ETDRS letter score visual acuity at 24 weeks 1326 1327 • Visual acuity AUC between randomization and 24 weeks • Mean change in OCT CSF thickness, adjusted for thickness at time or randomization, 1328 1329 using ITT, and per-protocol analyses • Percent of eyes with ≥ 1 and ≥ 2 logOCT step gain or loss in CSF thickness at 24-week 1330 1331 visit • Percent of eyes with OCT CSF thickness (in micros) < the following gender and OCT 1332 machine-specific values at 24-week visit: <290 in women and <305 in men in Zeiss 1333 1334 Cirrus; <305 in women and <320 in men in Heidelberg Spectralis • OCT CSF thickness area under the curve (AUC) between randomization and 24 weeks 1335 • Percent of eyes with worsening or improvement of diabetic retinopathy on clinical exam 1336 1337

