
1338

1339 7.4.1 Secondary Outcomes Analysis

1340 Analyses of secondary outcomes will be conducted as follows:

1341 Binary outcomes will be analyzed using logistic regression to control for baseline level of the

1342 outcome. Continuous outcome comparisons will be performed using ANCOVA with adjustment

1343 for baseline values. All linear model assumptions will be verified including linearity, normality

- 1344 of residuals, and homoscedasticity. If model assumptions are not met, a nonparametric analogue
- 1345 for ANCOVA will be considered. Multple imputation method will be implemented for missing 1346 data. GEE will be used to adjust for correlation between eyes of participants with two study
- 1347 eyes.
- 1348
- 1349

1350 7.5 Safety Analysis Plan

1351 Adverse events will be categorized as study eye, non-study eye, and systemic. The events will be tabulated and compared between treatment groups. Separate analyses will compare related adverse 1352

- 1353 events between groups.
- 1354
- 1355 Specific adverse events of interest will include:
- 1356 Injected-related: increased intraocular pressure, endophthalmitis, retinal detachment, retinal tears, intraocular hemorrhage 1357
- Ocular drug-related: increased intraocular pressure, need for ocular anti-hypertensives, 1358
- 1359 glaucoma surgery or other IOP-lowering procedures, development or worsening of cataract 1360 and cataract extraction, intraocular hemorrhage, inflammation, migration of Ozurdex to the anterior chamber and subsequent corneal complications 1361

1362 Systemic drug-related: Deaths, participants with at least one hospitialization, participants

with at least one SAE, and cardiovascular events and cerebrovascular events as defined by 1363 Antiplatelet Trialists' Collaboration 1364

1365 1366 • Systemic adverse events for participants with two study eves will be evaluated separately from participants with one study eye.

- 1367
- 1368

1369 Further definitions of the events for analysis and the analytic approach will be provided in the 1370 detailed statistical analysis plan.

1371 1372

1373 7.6 Additional Analysis Objectives Related to Design of Phase III Trial

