 - Footnote No. of missing values and No. of values truncated at 3 standard deviation from the mean (if any)¹
 - Review lens status for eyes improved or worsened on visual acuity at 24 weeks [Discussion text]
 - iii. Area under the curve (AUC) between randomization and 24 weeks using truncated data [Figure 2]
 - Mean \pm SD
 - Median [IQR]
 - Note: AUC is computed only for those completing the 24 week follow-up visit.
 - b. Compare change in visual acuity at 24 weeks from randomization between treatment groups
 - Perform Markov Chain Monte Carlo multiple imputation² on missing data (100 imputations) for change in visual acuity at 24 weeks using all available visual acuity data at post randomization follow-up visits, accounting for treatment group assignment, randomization visual acuity value, laterality and improvement in visual acuity during run-in phase. Create flags for binary outcomes specified above based on imputed data.

- ii. Primary analysis: Perform a linear mixed effects model for treatment group comparison of mean change in visual acuity at 24 weeks from randomization. (%*MIAnalyzeMeanMixed* macro)
 - Truncated change in visual acuity letter scores at 24 weeks will be fitted as the dependent variable, and the treatment group as the independent variable, adjusting for randomization visual acuity value, randomization stratification factors (laterality and improvement in visual acuity during run-in phase as defined in the protocol) by including each as a fixed effect in the model. A random subject effect will be included to adjust for the correlation between eyes of participants who have two randomized eyes (assuming a compound symmetry covariance structure).
 - Run the model on observed data to check model assumptions including residual analysis, goodness of fit and influence diagnostics [**not in text**]
 - Run the model on the imputed datasets and report the adjusted mean difference, 95% confidence interval, and *P*-value from treatment group comparison [**Table 2**]
 - Assessment of confounding: Impute the outcome accounting for additional pre-specified potential confounding factors, including age, duration of diabetes, HbA1c levels, retinal thickening on OCT, and diabetic retinopathy severity on clinical exam. All categorical covariates with more than 2 levels are collapsed to a binary covariate for modeling to aid convergence. Mimic primary analysis and obtain *P*-value for treatment group comparison.

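### Visual acuity AUC and CST AUC are compared in 24-week completers without imputation, although Protocol 7.4.1 prescribes multiple imputation for secondary outcomes with no exemption; no reason is given, and the effect is small

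*SAP*

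**What the plan says.** Protocol 7.4 names two area-under-the-curve outcomes among the secondary outcomes: "Visual acuity AUC between randomization and 24 weeks" and "OCT CSF thickness area under the curve (AUC) between randomization and 24 weeks". Protocol 7.4.1, which governs the analysis of all secondary outcomes, states: "Multple imputation method will be implemented for missing" data. It names no outcome to which this does not apply. For the primary comparison, Protocol 7.3.1 says "The intent-to-treat analysis will include all randomized eyes".

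The SAP handles the two AUCs differently. Items 4.a.iii (visual acuity) and 5.a.iii (CST) each carry the note "AUC is computed only for those completing the 24 week follow-up visit". The comparisons in 4.b.iii and 5.b.iii reuse the linear mixed model of the main analysis, restricted to 24-week completers and without imputation. The week-24 change and the gain/loss outcomes beside them in Table 2 are analysed from 100 imputations. For acuity, item 4.b.i builds these "using all available visual acuity data at post randomization follow-up visits"; item 5.b.i does the same with CST data.

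Interim data should be plentiful. Protocol 4.6 schedules visits every 4 weeks. Protocol 4.7 adds "The following procedures will be performed at each protocol visit unless otherwise specified", and its list includes acuity and OCT. Protocol 5.7 asks participants who withdraw to attend a closeout visit with the same testing.

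**The concern.** An AUC over 24 weeks uses every visit, so it suffers least from one missing final visit. Yet under the SAP an eye without a week-24 visit contributes nothing to it, however much was observed before. The same eye's earlier visits do inform the imputed week-24 change. Table 2 would therefore set imputed comparisons of all randomized eyes beside completer comparisons, against a protocol rule that makes no such distinction.

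Two things are at stake: a little precision, and some protection against bias if the eyes lost from one arm differ in acuity or thickness from those that stay. Neither the primary acuity analysis nor the comparison of mean CST change is affected.

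**Working it through.** **1. The texts side by side**

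| | Protocol 7.4 and 7.4.1 | SAP |
|---|---|---|
| Visual acuity AUC | Secondary; impute | Completers only, no imputation (4.a.iii, 4.b.iii) |
| CST AUC | Secondary; impute | Completers only, no imputation (5.a.iii, 5.b.iii) |
| Reason for the difference | – | None in the supplied text |

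**2. The protocol's own figures**

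Protocol 7.2 has 70 evaluable eyes per group, raised to 75 for about 5% loss. The half-width 1.96 × SD × √(2/70) is 2.32 letters for SD 7 and 2.98 for SD 9, against the stated 2.3 and 3.0. Power for 5 letters with SD 9 is Φ(5/(9√(2/70)) − 1.96) = Φ(1.33) = 0.908, against the stated 90%. These concern week-24 change; the documents give no SD for either AUC.

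**3. Information discarded**

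The share of follow-up time observed is last visit/24: week 4, 16.7%; week 8, 33.3%; week 12, 50.0%; week 16, 66.7%; week 20, 83.3%. All such eyes are dropped.

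**4. Precision**

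Planned loss is 0.05 × 150 = 7.5 eyes, or 2 × (75 − 70) = 10. Relative to all 75 eyes per arm, the completer standard error rises by √(75/71.25) = 1.026 to √(75/70) = 1.035. This is a ceiling, because imputation recovers only part of what is lost. In the simulation in step 6, random loss gave ratios of 1.022 to 1.032.

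**5. Scale of the acuity AUC (assumptions)**

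Assume change from randomization averaged over 24 weeks by the trapezoid rule, SD 7 at every visit, and a common between-visit correlation r. The weights are five of 1/6 and one of 1/12; they sum to 11/12 and their squares sum to 21/144 = 0.1458.

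SD = 7 × √(r(11/12)² + (1 − r) × 0.1458) = 4.92 (r = 0.5) or 5.57 (r = 0.7).

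95% half-width, 1.96 × SD × √(2/n):

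| r | n = 75 | n = 71.25 | n = 70 |
|---|---|---|---|
| 0.5 | 1.57 | 1.61 | 1.63 |
| 0.7 | 1.78 | 1.83 | 1.84 |

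**6. Bias (simulation)**

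Assumptions: 75 eyes per arm, one eye per participant, no true difference, 4 or 5 eyes lost per arm, last visit uniform over weeks 4 to 20. There were 1,500 replicates and 20 imputations by sequential Bayesian regression on arm and earlier visits. Outcome-related loss has weight exp(−0.8 × change/7). The last row is a separate completer-only run of 8,000 replicates. Bias in the AUC difference, in letters, over r = 0.5 and 0.7:

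| Loss | Completers | Imputed |
|---|---|---|
| Random | −0.004 to 0.003 | −0.001 to 0.002 |
| One arm related to last observed change | 0.160 to 0.262 | 0.000 to 0.002 |
| One arm related to next, unseen change | 0.159 to 0.253 | 0.029 to 0.054 |
| Same outcome-related loss in both arms | under 0.005 | not run |

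Against the matching half-width, the second row runs from 0.160/1.61 = 10% to 0.262/1.84 = 14%. In AUC SD units it is 0.160/4.92 = 0.03 to 0.262/5.57 = 0.05.

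Cross-check: bias equals the fraction lost times the gap between completers and lost eyes. The simulated values correspond to gaps of 0.160/(4/75) = 3.0 to 0.262/(5/75) = 3.9 letters.

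**7. Bilateral participants**

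The protocol expects 20% of about 125 participants, that is 25, to have two study eyes, one in each arm. Losing such a participant removes an eye from both arms. With 25 such pairs and an assumed between-eye correlation of 0.3 to 0.5, the one-arm completer bias fell by about 7% to 18%.

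**The case against.** The strongest reply is that the governing document is not in view. Protocol Chapter 7 calls itself a framework for a later, detailed plan. The supplied SAP is a manuscript technical plan that points to version 2 of the protocol SAP. If version 2 contains the completer rule, little more than a missing reference and reason remains. This stands, and it limits the finding to an unexplained departure within the supplied documents.

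A second reply is that the bias figures are selective. This also stands in part: they need outcome-related loss in one arm only, which no document suggests, and one eye per participant. They are near the worst case for the assumed strength of selection.

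Four stronger readings are tempting and are not supported:

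- **That the restriction was chosen after seeing data.** The technical plan took effect on 9-25-2017 and uses a database dated 21 September 2017, but the cited version 2 carries earlier dates and may already contain the rule.
- **That the handling of a completer's missed interim visits is undefined.** The dataset documentation the plan refers to was not supplied, and part of the plan's text was not available to this review. Silence cannot be shown.
- **That the CST-threshold outcome is a further fault.** It too is analysed from observed data, but items 5.a.i and 5.b.iii both say so explicitly. Nothing more is asked there.
- **That the trial's main conclusion is at risk.** The primary acuity analysis is imputed and untouched.

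**Conclusion.** The departure is real on the text: two secondary outcomes that Protocol 7.4.1 says will be imputed are analysed in completers only, with no reason in the supplied documents. The consequence is small. The standard error is at most 2.6% to 3.5% larger at the planned loss. Bias is about zero with random loss or with the same outcome-related loss in both arms. With one-arm, outcome-related loss and one eye per participant it is about 0.16 to 0.26 letter, 10% to 14% of the half-width, and somewhat less once bilateral participants are counted.

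The letter figures rest on the assumed SD of 7, correlations of 0.5 to 0.7 and the trapezoid average. They scale with the fraction lost and with the gap between lost and retained eyes. For CST AUC only the SD-unit figure (0.03 to 0.05) carries over, under the same assumptions, because the documents give no CST SD.

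The change is still worth making because the protocol already calls for it and it needs no new data. Confidence is medium, because version 2 of the protocol SAP has not been seen.

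**What to change.** Make both AUC comparisons follow Protocol 7.4.1:

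- Keep the imputed values at all post-randomization visits from the 100 imputations, not only week 24.
- Apply the same truncation, compute both AUCs for all randomized eyes, fit the same mixed model, and pool with Rubin's rules.
- For CST AUC, include randomization CST in the imputation model. Item 5.b.i lists randomization visual acuity instead, although the CST analysis model adjusts for randomization CST, so the CST imputations cannot be reused as written.
- Keep the completer analysis as a sensitivity analysis.

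If version 2 of the protocol SAP authorises the completer restriction, cite the clause with its reason and add the imputed AUC as a sensitivity analysis.

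The cost is some SAP wording and extra programming. The imputed AUC relies on data being missing at random. In the simulation where that fails, it keeps a bias of 0.03 to 0.05 letter, about 14% to 28% of the completer bias. The simulation had no baseline covariate, so it does not test the CST imputation model directly.
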